7.0 STUDY PARAMETERS

Patients will be block randomized by clinic, sex, and alcohol use severity to control for demographics at a 1:1:1 ratio to be in the self-monitoring, peer-supported Tula, or clinically integrated Tula groups. It's anticipated that 3-7 clinics (defined as having at least 10 patients in the study) with 3-7 clinicians each and 546 patient subjects will be recruited from the participating UW Health clinics. Patients will have access to Tula for up to 48 months, depending on time of enrollment, although the active period of participation is defined as 3 months with follow up through 12 months post enrollment (9 month follow-up). Health coaches will have access to patient-shared Tula data from patients of the clinically integrated Tula group for the duration of the study. The peer mentor will have access to discussion boards and private messages on Tula for the duration of the study for patients in the peer-supported

Protocol
HS IRB #2019-0337
Version 5. 10/17/19
Version 6. 04/07/20
Version 7. 10/09/20
Version 8. 01/26/21
Version 9. 08/18/21
Version 10. 07/13/23

group. The research team will have access to all Tula data for all subjects in all groups for the duration of the study.

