8.0 STATISTICAL CONSIDERATIONS

Analyses will assess the effectiveness between the three groups longitudinally on the primary and secondary outcomes.

Descriptive analyses. The research team will use descriptive statistics for all demographic and clinical variables across all three arms. To assess the impact of chance baseline imbalances between arms on intervention effect estimates, variables with noticeable differences will be included as covariates in a sensitivity analysis.

Intervention analyses. The analysis assesses direct treatment effects on patient outcomes over time over the 12-month study period. The research team will construct a longitudinal model of our outcome measures at 0, 1, 2, 3, 4, 5, 6, 7, 8, 9, 10, 11, and 12 months after randomization. The stratification variables will be by clinic, biological sex, and alcohol severity. They will be included as factors in the model and the baseline values of patient outcomes will be included as covariates, with a separate model for each primary outcome (risky drinking patterns, quality of life, and cost). This longitudinal analysis is complicated by the dependence among successive observations made on the same individual. Since complete control of measurement is not possible, there may be incomplete data from individual subjects. Therefore we will conduct a mixed-model analysis of repeated measures based on the general linear model with assessment of various covariance structures (compound symmetric, autoregressive order one, and unstructured). Covariance structure selection will be based on Akaike's information criterion and Schwarz's Bayesian criterion.^{46, 47} Pairwise comparisons between treatment groups and specific treatment time contrasts in the mixed model will be conducted to respond to between-group effects and time-based effects. To address issues of incomplete data we plan to estimate treatment effects according to 4 approaches: intention-to-treat, as-treated, per-protocol, and complier-average causal effect. Missing data patterns will be established from the longitudinal data and will be used to adjust the longitudinal intervention analysis according to pattern-mixture modeling.⁶⁹

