Power. Power calculations are based on the previous randomized clinical trial of the platform.⁷¹ The study is powered to detect a difference between groups in risky drinking episodes across the 12-month intervention period. Based on the attrition rate in the previous randomized clinical trial of Tula, we assume an attrition rate of 23% over the course of the study. To detect an effect size of Cohen's $d=0.23$ the research team will recruit 182 patients per group (546 patients total) to have sufficient power ($1-\beta=0.8$, multiple comparison adjusted $\alpha=0.0167$, two-tailed). This would be a difference of 1.37 risky drinking episodes per month.

Quantitative data collection. The data collected in will come from multiple sources (see Table 1). Data collected from patient surveys will be collected by the Tula system and securely stored on CHESS servers. All log files will be stored on the CHESS server to be used to assess Tula use.

Qualitative data collection. This project will make use of clinician interviews to better understand the effect of Tula in the primary care setting. The interview will occur at intervention month 36 and take place at the clinicians' primary care clinic. Qualitative researchers will ask clinicians to talk about their experiences with Tula to refine the system for future use in primary care.

Qualitative data analysis. Content analysis will describe how Tula use can improve patient outcomes; identify potential improvements in Tula; and identify how qualitative data can supplement the quantitative analysis. A qualitative researcher will construct a coding scheme to assess the ideas of the study in order to capture references to a concept. The analyses will help the research team refine Tula for future dissemination by determining the individual and organizational conditions necessary to promote effectiveness.

Protocol

HS IRB #2019-0337
Version 5. 10/17/19
Version 6. 04/07/20
Version 7. 10/09/20
Version 8. 01/26/21
Version 9. 08/18/21
Version 10. 07/13/23

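### If the planning level of 0.0167 is also the final threshold for all three arm comparisons, a Shaffer step-down would give more power at the same 5% familywise error

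*Combined protocol and SAP*

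**What the plan says.** Section 7.0 (Study Parameters) allocates patients "at a 1:1:1 ratio to be in the self-monitoring, peer-supported Tula, or clinically integrated Tula groups", which gives three possible arm pairs.

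Section 8.0, Power, states: "The study is powered to detect a difference between groups in risky drinking episodes across the 12-month intervention period". The inputs are Cohen's d of 0.23, power of 0.8, attrition of 23% and "multiple comparison adjusted $\alpha=0.0167$, two-tailed". On that basis, "the research team will recruit 182 patients per group (546 patients total").

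Section 8.0, Intervention analyses, states: "Pairwise comparisons between treatment groups and specific treatment time contrasts in the mixed model will be conducted". It gives no significance level for these comparisons and describes no global test, ordering, step-down or closed procedure. It does not define which arm parameter is tested: a difference averaged over visits, an arm-by-time effect or a month-12 difference. The same paragraph names three primary outcomes (risky drinking patterns, quality of life and cost), each with its own model.

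The value 0.0167 therefore appears once, as a sizing input, and is the only threshold available for the pairwise comparisons.

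**The concern.** 0.05/3 is the single-step Bonferroni level for three tests. Applied to all three pairs among three arms, it ignores a logical constraint: the three pairwise nulls cannot be true or false independently. If two arms differ, the third cannot equal both of them, so at most one of the remaining nulls is true. A procedure that uses this constraint controls the familywise error at the same 5% and rejects more false nulls.

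The loss would fall on the second and third comparisons. The primary aim is stated across all three groups, and Section 8.0 bases its main cost-effectiveness ratio on the clinically integrated versus peer-supported contrast. If both Tula arms beat self-monitoring, showing this takes two rejections, not one.

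**Working it through.** **Inputs.** Three arms at 1:1:1 (Section 7.0). Two-sided level 0.0167, power 0.80, d = 0.23, 182 per group, 23% attrition (Section 8.0, Power). The documents do not give the true pattern of the three means, so several are shown.

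**The plan's own figures.** 0.05/3 = 0.01667, so the level is reproduced. The sample size is not reproduced by a simple two-sample formula: n = 2(z₀.₉₉₁₆₅ + z₀.₈₀)²/d² = 2(3.235)²/0.23² = 396 per group before attrition, against 182. An unstated gain from repeated measures could close that gap: a compound-symmetry correlation of roughly 0.14 to 0.42, depending on the number of visits and on whether 140 completers (182 × 0.77) or all 182 are analysed. The sample size is a separate question. Here the stated 80% is taken as given, and the result is then repeated without it.

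**Design point.** A pair with 80% power at two-sided 0.0167 has noncentrality z₀.₉₉₁₆₅ + z₀.₈₀ = 2.393 + 0.842 = 3.235.

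**Procedures compared** (normal test statistics, equal arms, at least 1,000,000 simulated trials per pattern):
- Flat: each pair rejected if |Z| > 2.394 (level 0.05/3).
- Shaffer: if the largest |Z| > 2.394, every pair with |Z| > 1.960 is rejected.
- Closed 2-df: if the global chi-square exceeds 5.99, every pair with |Z| > 1.960 is rejected.

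**Familywise error**

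| True state | Flat | Shaffer | Closed 2-df |
|---|---|---|---|
| All three arms equal | 0.044 | 0.044 | 0.050 |
| One pair equal, third arm differs by 0.23 | 0.017 | 0.049 | 0.050 |

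In the second row the flat rule uses only a third of the 5% allowance.

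**Power**

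| Pattern of means | Quantity | Flat | Shaffer | Closed 2-df |
|---|---|---|---|---|
| One arm differs by 0.23 from two equal arms | each true pair | 80.0% | 86.4% | 87.7% |
| | both true pairs | 68.7% | 81.4% | 82.7% |
| | at least one rejection | 91.3% | 91.3% | 92.7% |
| Graded: extremes differ by 0.23, middle arm halfway | each neighbouring pair | 22% | 35% | 36% |
| | extreme pair | 80.0% | 81.3% | 82.7% |
| Equally spaced, 0.23 between neighbours | each neighbouring pair | 80.0% | 89.9% | 89.9% |

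As an analytic check on the graded pattern, a neighbouring pair has noncentrality 3.235/2 = 1.618, and P(Z > 2.394 − 1.618) = P(Z > 0.776) = 0.219.

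**Without the stated 80%.** Treating the trial as a simple comparison of 182 per group, the noncentrality is 0.23 × √(182/2) = 2.194 and flat power is 42%. With 140 completers per group it is 0.23 × √70 = 1.924, and flat power is 32%. When one arm differs, Shaffer raises these to 49% and 38% per true pair.

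**Does either alternative ever lose a flat rejection?** Shaffer cannot, because its first step is the flat rule. The closed 2-df test can: 2.394² = 5.73 is below 5.99, so a pair can pass 0.0167 while the global test fails. This happened in about 0.2% to 0.4% of simulated trials in three of the four patterns examined (all equal, one arm differs, graded).

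**The case against.** **The plan does not say that the final tests use 0.0167.** A reader might infer that the trial will test all three pairs at a flat Bonferroni level and so will waste power. The documents do not establish this. Bonferroni is not named, the figure is a sizing input, and sizing at 0.05/3 is compatible with a later step-down whose first step is 0.05/3. This objection stands, and the point is conditional for that reason. What remains is that no other threshold is given, so an analyst following the text would most naturally use 0.0167 throughout.

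**The divisor could be outcomes.** Three primary outcomes are listed, so 0.05/3 could be a correction across outcomes. The reference to multiple comparisons, and a power statement about a difference between groups on a single outcome, favour pairs but do not settle it. If outcomes were meant, testing at 0.05 within each would remove the only correction the plan states, and error across three independent outcomes could reach 1 − 0.95³ = 14%. This stands and shapes the fix.

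**The family may be larger than three.** The sentence on pairwise comparisons also covers treatment-by-time contrasts. Shaffer's argument applies to three hypotheses on one arm parameter, which must first be named. This also stands.

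**The flat rule is valid, simple and has matching intervals.** This is true: the point is an efficiency gain, not an error of validity. A reader might also infer that a 2-df global test followed by pairs at 0.05 is interchangeable with Shaffer, or that power rises across the board. Neither is so. The global test is slightly more powerful on average but can lose a flat rejection. Shaffer leaves the chance of at least one rejection unchanged and barely moves the largest difference.

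**A late change costs credibility.** Section 4.0 mentions participants who have completed 12 months, and Section 7.0 gives the research team access to all Tula data in all groups. The rule must therefore be settled before outcomes are examined by arm.

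**Conclusion.** The point holds conditionally, as an inexpensive improvement. If 0.0167 is the correction for three arm pairs and would be applied flat to the final tests, Shaffer's step-down dominates it within an outcome: familywise error stays at or below 5%, no flat rejection is lost, and the second and third pairs gain power. Taking the stated 80% at face value, the per-pair gain is about 6 points when one arm differs (80% to 86%), 13 points for neighbouring pairs under graded effects (22% to 35%), and about 1 point for the extreme pair. If the true power is nearer 32% to 42%, the per-pair gain when one arm differs is about 6 to 7 points. These sizes rest on an assumed pattern of means, equal arms and normal test statistics. The documents do not support saying that the trial has committed itself to a wasteful test, and nothing here bears on multiplicity across the three primary outcomes.

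**What to change.** Add to Section 8.0:
1. A statement that 0.0167 is the correction for the three arm pairs, if that is what was meant.
2. One pre-specified arm contrast per outcome, kept separate from the treatment-by-time contrasts.
3. The testing rule within an outcome: the smallest of the three pairwise p-values is compared with 0.05/3; if it rejects, the other two are each tested at two-sided 0.05; otherwise testing stops.

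Keep 182 per group and describe 0.0167 as the planning threshold. Date the rule before any outcome is examined by arm.

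If 0.0167 was meant as the level for each of three primary outcomes, run the step-down inside it: 0.0167/3 = 0.0056 for the smallest p-value, then 0.0167 for the other two. In either case, multiplicity across outcomes needs its own statement.

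A 2-df arm test at 0.05 followed by pairs at 0.05 is an acceptable alternative if the small risk of losing a flat rejection is accepted.

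The cost is a few sentences, including the choice of contrast, with no change to sample size or data collection. The step-down tests no longer correspond one-to-one with simple simultaneous confidence intervals; Bonferroni intervals for the three differences can be reported alongside.
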